8.2 Primary Endpoints (Safety and Effectiveness)

- 100% agreement and validation of specific tissue features on VIO images (epidermis, dermis, collagen, blood vessels and pigment) in comparison to gold standard pathology images in Comparative Reader assessment.
- >90% agreement between Blinded Reader VIO image assessment and answer key developed from validation assessment.
- Safety will be assessed as the incidence of all adverse events (analyzed by severity, seriousness, and relationship to the device and procedure) that occur through the 7-day follow-up period.

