8.3 Secondary Endpoints

- 90% inter-reader agreement
- Evaluation of secondary histopathology characteristics

9 Study Design

This study is a prospective, multicenter, single-arm clinical investigation with 3 stages:

1. Procurement of training samples and development of training materials
2. Procurement of test samples and validation of Enspectra Health Images with Ground Truth Pathology (comparative reader assessment) *
3. Performance testing (blinded reader assessment of Enspectra Health images) *

*Training samples will not be used for validation or performance testing.

10 Subject Selection

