13.1 Sample Size Determination

The sample sizes of 20 subjects for the training set and 30 subjects for the validation set were determined by simulation studies (see Appendix A). The goal of these studies was to select sample sizes with a high probability of representation in as many of the subgroups of interest as possible. These sample sizes provide a $> 90\%$ chance of representation for underlying conditions of interest and Fitzpatrick skin type groups. In addition, these sample sizes reliably provide variability across age groups, genders and lesion locations.

If areas are assumed to be independent, the sample size of at least 360 areas in the validation set will produce confidence intervals with a width of $\pm 6.2\%$. The areas are correlated, which decreases precision, but the number of areas is expected to be larger, which increases it. If these factors offset, a confidence interval width of $\pm 6.2\%$ is a reasonable estimate of the expected results.

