13.2.3 Comparison of Validation Set to Ground Truth Histology

First, an expert reviewer and 2 comparative reviewers will assess each of the VIO images, blinded to the histopathology results. For each area, the reviewer will classify the predicted primary histopathology characteristics according to the categories described in section 11.4. Second, the expert reviewer will determine the actual primary histopathology characteristics based on the histopathology results. Third, the predicted characteristics will be compared to the expert reviewer classification.

An iterative review process will be performed until there is complete consensus across all reviewers. The output of this iterative review process will be an “answer key” that reflects 100% consensus of the comparative results from the VIO image and pathology across all 3 comparative readers. Achieving 100% agreement/concensus through this process satisfies the first Primary Endpoint.

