13.2.4 Performance Testing of Blinded Readers

Once the answer key is finalized for the validation set, 3 blinded readers will be used for performance testing. The blinded readers will be trained using the training set, and will then be provided with the VIO images only from the validation set. Each blinded reader will classify the primary histopathology features and regions for each of the approximately 360 areas in the validation set and identify secondary histopathology characteristics in each VIO image.

Accuracy will be assessed for primary histopathology characteristics only, compared to the answer key, as the proportion of total points for each of the blinded reviewers as described in section 11.5.

The accuracy assessment will be performed using a conditional, generalized linear mixed model (GLMM) to account for correlation among multiple images obtained for the same subject, and for correlation of responses within each reviewer. Once each response has been scored, the data will be condensed to 1 record per patient per reviewer. The dependent variable will be the number of points obtained divided by the maximum number of points possible. The GLMM will use a binomial response distribution and a logit link function. A compound symmetry variance-covariance matrix will be used to account for correlation. Random effects will be included for each subject-reviewer cluster. Reviewer will be included as a model covariate, and the correlation-adjusted proportion correct will be calculated separately for each reviewer by applying the standard logistic function to the least-square means by reviewer. This GLMM framework (with an intercept term) will be used to produce overall and reviewer-specific point estimates and 95% confidence intervals. The point-estimate target for overall accuracy is 90%.

Inter-rater agreement among the BRs will be assessed using Kappa statistics, and the target for agreement is 90%. Overall accuracy compared to the answer key across the subgroups will be assessed by adding each subgroup to the GLMM as a categorical variable. Accuracy for secondary histopathology characteristics may also be reported, but there are no *a priori* targets.

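### Does it matter that the 90% inter-reader agreement target is assessed with kappa, without the scale being spelled out?

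*Combined protocol and SAP*

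**What the plan says.** Section 8.3, like the study summary in section 3, lists the secondary endpoint as "90% inter-reader agreement" and names no statistic.

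Section 13.2.4 gives the analysis rule: "Inter-rater agreement among the BRs will be assessed using Kappa statistics, and the target for agreement is 90" percent. It does not name the kappa (averaged pairwise Cohen, Fleiss or another), although "3 blinded readers will be used for performance testing". It also does not say whether the 90% is a value of kappa or of raw agreement.

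The accuracy target in the same section is more explicit: "The point-estimate target for overall accuracy is 90" percent, on a defined proportion of points.

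On what is rated, section 13.2.4 says: "Each blinded reader will classify the primary histopathology features and regions for each of the approximately 360 areas in the validation set". Section 13.2.3 has areas classified "according to the categories described in section 11.4". Sections 11.4 (categories) and 11.5 (scoring) are not in the released text. Section 11.3.3 is blacked out just where it begins to describe what the blinded readers assess.

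**The concern.** A percentage of agreement and a kappa coefficient are different quantities. Kappa subtracts the agreement expected by chance, so it is below raw agreement whenever agreement is incomplete. A target written as a percentage and attached to kappa can be read two ways: kappa of at least 0.90, or raw agreement of at least 90% with kappa reported beside it.

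Two things would be at stake. Readers who meet the endpoint as sections 3 and 8.3 word it could be reported as missing it. And if the scale is not settled before the blinded reads are analysed, it could be chosen once the results are known.

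**Working it through.** **Inputs from the plan.** Three blinded readers and about 360 areas (13.2.4; 13.1 gives "the sample size of at least 360 areas in the validation set"); target 90%. Section 8.2 names five features: "specific tissue features on VIO images (epidermis, dermis, collagen, blood vessels and pigment"). The 90% is a bare threshold with no derivation, so there is no figure to reproduce.

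**Assumed inputs.** Rating format and category shares are not in the released text, so a range is shown.

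**Formula.** With raw pairwise agreement Po and chance agreement Pe (sum of squared category shares), kappa = (Po − Pe)/(1 − Pe). Setting kappa to 0.90 gives Po = 0.90 + 0.10 × Pe.

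| Assumed format | Pe | Kappa when Po = 0.90 | Po needed for kappa 0.90 |
|---|---|---|---|
| 5 categories, equal | 0.200 | 0.70/0.80 = 0.875 | 92.0% |
| 5 categories, 40/30/15/10/5 | 0.285 | 0.615/0.715 = 0.860 | 92.9% |
| 5 categories, 60/20/10/5/5 | 0.415 | 0.485/0.585 = 0.829 | 94.2% |
| Yes/no, 50/50 | 0.500 | 0.40/0.50 = 0.800 | 95.0% |
| Yes/no, 80/20 | 0.680 | 0.22/0.32 = 0.688 | 96.8% |
| Yes/no, 90/10 | 0.820 | 0.08/0.18 = 0.444 | 98.2% |

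A finer scheme narrows the gap: ten equal categories give Pe = 0.10 and need 91.0%.

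**Direction.** Po − kappa = Pe(1 − Po)/(1 − Pe), which is never negative. Reads with Po between 0.90 and 0.90 + 0.10 × Pe pass on mean pairwise agreement and fail on kappa. The reverse cannot occur.

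**A worked set of reads.** Take 360 areas with one dissenting reader in 50 of them. One dissenter breaks two of the three reader pairs, so mean pairwise agreement is 1 − 50 × (2/3)/360 = 90.7%. Fleiss kappa is (0.907 − 0.200)/0.800 = 0.884 for five balanced categories and (0.907 − 0.500)/0.500 = 0.815 for a balanced yes/no call. The percent scale passes and the kappa scale fails. Agreement of all three readers together is 310/360 = 86.1%, so percent agreement itself needs a definition.

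**How often the two readings would differ.** Simulation with 2,000 runs per case, three readers and 360 independent areas. Each reader copies a latent label with probability √kappa and otherwise draws from the category shares. Chance of passing on percent agreement and failing on Fleiss kappa, in the order of the table:

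- True agreement 93%: 19%, 42%, 86% (five categories); 97%, 99.6%, 99.6% (yes/no).
- True agreement 95%: 0.2%, 2%, 18%; 55%, 99%, 100%.

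At 97% the five-category cases no longer differ, while yes/no at 90/10 still differs in 97% of runs. At 85% essentially no run passes on either scale. The result therefore depends on the assumed format and on where true agreement falls.

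**The case for a change.** The strongest case for a change is that the mismatch is real whichever reading is right. If kappa of at least 0.90 is meant, sections 3 and 8.3 describe something easier than what is assessed. If raw agreement is meant, section 13.2.4 names the wrong statistic. The accuracy target nearby shows that the authors could tie a target to a defined quantity, and one or two sentences would settle the matter at no cost in data.

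The algebra in that case stands, and so does the observation that the kappa variant is unnamed. Three things weaken the call for a change. First, sections 3 and 8.3 are one-line labels; the sentence in 13.2.4 names kappa and gives the target in the same breath, and no other agreement statistic appears in the released text. Second, the obvious amendment would move the target to percent agreement. That takes it off the only statistic the plan names and onto one that is easier to reach when one category dominates, which many statisticians would resist. The alternative, restating the endpoint as a kappa value, only writes down what 13.2.4 already implies. Third, part of the definition may sit in the blacked-out text of 11.3.3 or in sections 11.4 and 11.5. The cross-references suggest that 11.4 and 11.5 cover categories and accuracy scoring rather than the agreement target, so this is a possibility only.

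One limit applies to calling the kappa reading stricter: it holds against mean pairwise agreement, the quantity kappa is built on. Against agreement of all three readers at once it need not hold. With one dissenter in 40 areas and five equal categories, kappa is (0.926 − 0.200)/0.800 = 0.907, while all three agree in 320/360 = 88.9%. Nothing in the plan points to that definition.

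**Conclusion.** No change to the plan is needed. Read as written, section 13.2.4 asks for kappa of at least 0.90. Under the assumed formats this means raw pairwise agreement of 92.0% to 98.2% rather than 90%, so the reading errs on the cautious side and gives no false success against 90% mean pairwise agreement. The released text attaches no hypothesis test, power calculation or decision to this secondary target, and the primary endpoints do not depend on it.

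What remains is missing detail of an ordinary kind. With three readers an analyst would choose a multi-rater kappa such as Fleiss, fix it in the analysis specification before the blinded reads are analysed, and report raw agreement beside it. Anyone reading the results could then see both scales.

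The direction of the gap between kappa and mean pairwise agreement is algebra and does not depend on the assumptions. Its size does: rating format, category shares and equal marginals across readers are all assumed. The simulated rates also treat areas as independent, whereas section 13.1 says they are correlated. They are illustrations and not forecasts for this study.

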13.3 Subject Population(s) for Analysis

Analysis populations will differ based on the purpose of the analysis. The Safety Analysis Set will include all subjects for whom an attempt was made to image lesions using the VIO device. Adverse events, protocol deviations (PDs), device malfunctions and study disposition will be reported for this set. The Full Imaging data set will include all subjects in the safety set and all VIO images. The Primary Analysis Set will include only subjects with at least 4 images of sufficient quality to be included in the training or validation set, and only images of sufficient quality to be included in these sets. The Primary Analysis Set will be used for all other descriptive summaries and for analyses of accuracy and agreement. A comparison between the Full Imaging Set and the Primary Analysis Set will be used to summarize the rate of high-quality images.

14 Safety and Adverse Events

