6.1.1 Skin and device preparation

Prior to imaging, the lesion of interest and uninvolved skin site to be imaged must be cleaned thoroughly with an alcohol swab or soap and water to ensure the skin is free of residual ink, lotion, makeup etc. as this may disrupt imaging. The center hole of the targeting sticker is then placed over the center of lesion or skin site and secured firmly in place. A drop of pharmaceutical grade immersion fluid such as glycerin is applied inside this targeting sticker. The tip of the imaging wand is cleaned with an alcohol swab and a single-use imaging cover is placed onto the imaging tip. The imaging cover is also cleaned with an alcohol swab prior to imaging.

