14.1 Definitions

Adverse event

An adverse event (AE) is any untoward medical occurrence (i.e., any unfavorable and unintended sign, including abnormal laboratory findings, symptom, or disease) in a clinical investigation subject after written informed consent has been provided for participation in the study. Therefore, an AE may or may not be temporally or causally associated with the use of the device.

In the following differentiation between medical history and AEs, the term “condition” may include abnormal physical examination findings, symptoms, diseases, laboratory findings, and electrocardiogram findings.

- Conditions that started before signing of informed consent and for which no symptoms or treatment are present until signing of informed consent are recorded as medical history (e.g., seasonal allergy without acute complaints).

- Conditions that started before signing of informed consent and for which symptoms or treatment are present after signing of informed consent, at *unchanged intensity*, are recorded as medical history (e.g., allergic pollinosis).
- Conditions that started or deteriorated after signing of the ICF will be documented as AEs.

Serious adverse event (SAE)

Any untoward medical occurrence that, at any dose, meets any of the following criteria (a—g):

- a. Results in death.
- b. Is life-threatening.

The term ‘life-threatening’ refers to an event in which the subject was at risk of death at the time of the event, it does not refer to an event which hypothetically might have caused death if it were more severe.

- c. Requires inpatient hospitalization or prolongation of existing hospitalization.

A hospitalization or prolongation of hospitalization will not be regarded as an SAE if at least one of the following exceptions is met:

- The admission results in a hospital stay of less than 12 hours.
- The admission is pre-planned
(i.e., elective, or scheduled surgery arranged prior to the start of the study).
- The admission is not associated with an AE
(e.g., social hospitalization for purposes of respite care).

However, it should be noted that invasive treatment during any hospitalization may fulfill the criterion of ‘medically important’ and as such may be reportable as an SAE dependent on clinical judgment. In addition, where local regulatory authorities specifically require a more stringent definition, the local regulation takes precedence.

- d. Results in persistent or significant disability / incapacity.

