1	Not related	An event almost certainly caused by concurrent/underlying illness, drugs, procedure, or other causes.

*Note that an AE occurring before treatment with the study device will be categorized as unrelated to the study device.

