14.2 Reporting of Adverse Events

14.2.1 Assessments and documentation of adverse events

The Investigator or designee must collect all AEs for each subject from the time of the start of device procedure preparation to 7 days (\pm 3 days) following the end of subject study participation, whether or not deemed related to the investigational device or procedure. All AE data will be recorded on the CRF. All AEs will be followed until the event has subsided or, for a minimum of 30-days after subjects' participation has ended.

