14.4 Potential Risks to Study Subjects

The following are the possible risks associated with the VIO procedure:

- Irritation from adhesive targeting guide
- Allergic reaction such as irritation or sensitivity to immersion fluid or cover
- Pain due to pressure from the wand and/or sensitivity of the lesion
- Infection caused due to improper cleaning of the device

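### The Safety Analysis Set requires an attempt to image a lesion, so a subject exposed to the sticker or immersion fluid but stopped before that attempt is outside the planned safety summary

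*Combined protocol and SAP*

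**What the plan says.** The relevant text is spread over several sections of the combined protocol and SAP.

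- **Analysis set (13.3).** "The Safety Analysis Set will include all subjects for whom an attempt was made to image lesions using the VIO device". The next sentence reads: "Adverse events, protocol deviations (PDs), device malfunctions and study disposition will be reported for this set". The Full Imaging set is built from the safety set, so it brings in no further subjects.
- **Collection window (14.2.1).** "The Investigator or designee must collect all AEs for each subject from the time of the start of device procedure preparation".
- **AE definition (14.1).** An AE is an untoward occurrence "in a clinical investigation subject after written informed consent has been provided for participation in the study", which is earlier again.
- **Relatedness note (14.1).** Under the grading table: "an AE occurring before treatment with the study device will be categorized as unrelated to the study device".
- **Preparation (6.1.1).** The sticker is fixed over the lesion or skin site, and then: "A drop of pharmaceutical grade immersion fluid such as glycerin is applied inside this targeting sticker". Both steps come before the wand touches the skin (6.1.2).
- **Device components (6.1.5).** The imaging cover and the targeting stickers are named as the device parts that contact skin. Immersion fluid is not named.
- **Listed risks (14.4).** The first is "Irritation from adhesive targeting guide". The second is an allergic reaction to immersion fluid or cover.
- **Endpoint (8.2).** The primary safety endpoint is the incidence of all AEs, analysed by severity, seriousness and relationship to device and procedure.

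Neither *attempt* (13.3) nor *treatment* (14.1) is defined.

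**The concern.** Three clocks run in the safety plan: AEs are defined from consent, collected from preparation, and reported only for subjects who reach an attempt to image a lesion. Two of the four risks in section 14.4 involve materials applied before scanning, so exposure to the device procedure begins before a subject qualifies for the safety set.

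The gap matters because leaving the set can be a consequence of the AE. Section 12.9 allows withdrawal at any time if the investigator sees a safety hazard. A reaction that stops the procedure during preparation would remove both the event and the subject from the summary. That is an informative exclusion, and it biases AE incidence downward for a risk that the protocol anticipates.

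A second, smaller question concerns the relationship breakdown. If *treatment* is read as scanning, the note in section 14.1 classes a reaction that began during preparation as unrelated to the device, which sits badly with section 14.4.

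**Working it through.** The plan states no AE rate, threshold or power for safety, so there is no figure to reproduce. The check is a reading of the rules by case, followed by an illustration of size.

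**Cases**

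| Subject's course | In safety set (13.3)? | AE in all-AE incidence (8.2)? | Device relationship (14.1 note) |
|---|---|---|---|
| (a) Reaction in preparation, lesion imaging then attempted | Yes | Yes | May be set to unrelated if *treatment* means scanning |
| (b) Reaction in preparation, no attempt follows at either site | No | No | Not tabulated |
| (c) Uninvolved site imaged, stopped before the lesion | No, read literally | No | Not tabulated |

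Case (c) arises because section 12.6 images both sites without stating that the lesion must come first, while section 13.3 refers to lesions. Only (b) and (c) drop out of the planned summary. In (a) the event is counted and only its grade is in question.

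For (a), the sticker and the fluid differ. The sticker is a device component by section 6.1.5, so placing it can be read as the start of *treatment*, and the note would then not apply. The fluid is not named there, so the note bites more clearly on a fluid reaction.

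**Size (illustration)**

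Inputs: N = 65, the maximum enrolment (section 4), or N = 50, the planned total (10.1). Assumed: k subjects have a preparation reaction and no lesion-imaging attempt, with k = 1 to 3, and there are no other AEs. The current rule reports 0/(N − k). A set based on first contact reports k/N. Intervals are Clopper-Pearson 95%; with zero events the upper limit is 1 − 0.025^(1/n).

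| N | k | Current set | Set from first contact |
|---|---|---|---|
| 65 | 1 | 0/64 = 0% (0 to 5.6%) | 1/65 = 1.5% (0.04 to 8.3%) |
| 65 | 2 | 0/63 = 0% (0 to 5.7%) | 2/65 = 3.1% (0.4 to 10.7%) |
| 65 | 3 | 0/62 = 0% (0 to 5.8%) | 3/65 = 4.6% (1.0 to 12.9%) |
| 50 | 1 | 0/49 = 0% (0 to 7.3%) | 1/50 = 2.0% (0.05 to 10.7%) |

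Each excluded subject removes about 1.5 percentage points at N = 65 and 2.0 at N = 50. Section 12.4 counts only subjects with device use toward the sample size, so such a subject might also be replaced. The comparison at 65 would then be 0/65 against 1/66 = 1.5%, which is practically the same.

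**The case against.** A reader might infer that sticker and fluid reactions during preparation drop out of the primary safety endpoint in general. The documents do not support that. Section 13.3 defines a set of subjects, not a time window, so a preparation AE in a subject who is later imaged is counted. Nor does the unrelated note remove anything from the incidence of all AEs; it can affect only the breakdown by device relationship. That objection stands.

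Other points on the same side:

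- **Undefined terms can be read kindly.** Section 6.1.1 sits among the device's operating steps, so preparing the lesion could be taken as part of an attempt, and placing the sticker as treatment. This is fair, but a population rule should not depend on which reading is chosen.
- **The endpoint also covers relationship to the procedure.** The note concerns only the device, so a preparation reaction could still be reported as procedure-related. However, the only scale shown in section 14.1 grades relationship to the device and treats the procedure as an alternative cause, so no route for this is set out.
- **Subject protection does not depend on the analysis set.** Case report form recording (14.2.1), serious-event reporting (14.2.2) and the medical monitor (14.6) are not restricted to it. This stands; the gap is in the planned summary.
- **The event may be rare.** Section 10.3 excludes known allergy or increased sensitivity to silicone, adhesives or glycerin. The second listed risk also includes the cover, which is on the imaging tip. Section 12.9 does not say that skin has been prepared when a device is found non-operational. All of this limits any claim about frequency.
- **No success decision turns on it.** The safety endpoint has no threshold, hypothesis or comparator. This is correct.

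**Conclusion.** The concern holds in a narrow form. A subject whose preparation reaction stops the procedure before any lesion-imaging attempt, or who is imaged only at the uninvolved site, is exposed yet belongs to no set for which AEs are reported, and that exclusion can depend on the outcome. If the device fails after skin has been prepared and no attempt is held to have occurred, the same wording leaves the subject out of the malfunction and disposition tables.

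For subjects who are imaged after a preparation reaction, overall incidence is intact. The remaining issue is possible misclassification of device relationship, conditional on reading *treatment* as scanning, and clearest for immersion fluid.

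The size cannot be estimated from the documents. About 1.5 percentage points per subject at 65 is an illustration that assumes the case occurs and no other AEs are seen. The conclusion rests on the literal wording of sections 13.3 and 14.1, with both key terms undefined. It is a small defect that is worth correcting because correction is cheap, and it does not show that the safety endpoint is generally unsound.

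**What to change.** - **Section 13.3:** define the Safety Analysis Set as all subjects with first skin contact of sticker, immersion fluid, cover or wand, at the lesion or the uninvolved site. Keep attempted imaging as the denominator for image-quality summaries only, and say what counts as an attempt.
- **Section 14.1, relatedness note:** apply the automatic unrelated category only to AEs that begin before that first contact, and grade later AEs on the scale. This replaces the undefined term *treatment*.
- **Sections 13.3, 14.1 and 14.2.1:** reconcile the three starting points (consent, preparation, imaging attempt), and state how an AE between consent and first contact is listed.

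The cost is a few sentences, with no extra visits, data or subjects. The safety denominator and the device-related count may rise slightly.
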